10.2.2 Definitions

IU.Z.Z Dellilli	lions
Additional study treatment	Medicinal products that may be used during the clinical trial as described in the protocol, but not as an investigational medicinal product (e.g. any background therapy)
Assessment	A procedure used to generate data required by the study
Biologic Samples	A biological specimen including, for example, blood (plasma, serum), saliva, tissue, urine, stool, etc. taken from a study participant
Cohort	A specific group of participants fulfilling certain criteria and generally treated at the same time
Control drug	A study drug (active or placebo) used as a comparator to reduce assessment bias, preserve blinding of investigational drug, assess internal study validity, and/or evaluate comparative effects of the investigational drug
Dosage	Dose of the study treatment given to the participant in a time unit (e.g. 100 mg once a day, 75 mg twice a day)
Electronic Data Capture (EDC)	Electronic data capture (EDC) is the electronic acquisition of clinical study data using data collection systems, such as Web-based applications, interactive voice response systems and clinical laboratory interfaces. EDC includes the use of Electronic Case Report Forms (eCRFs) which are used to capture data transcribed from paper source forms used at the point of care
End of the clinical trial	The end of the clinical trial is defined as the last visit of the last participant or at a later point in time as defined by the protocol
Enrollment	Point/time of participant entry into the study at which informed consent must be obtained
Estimand	A precise description of the treatment effect reflecting the clinical question posed by the trial objective. It summarizes at a population-level what the outcomes would be in the same patients under different treatment conditions being compared. Attributes of an estimand include the population, variable (or endpoint) and treatment of interest, as well as the specification of how the remaining intercurrent events are addressed and a population-level summary for the variable.
Healthy volunteer	A person with no known significant health problems who volunteers to be a study participant
Intercurrent events	Events occurring after treatment initiation that affect either the interpretation or the existence of the measurements associated with the clinical question of interest.
Investigational drug/ treatment	The drug whose properties are being tested in the study
Medication number	A unique identifier on the label of medication kits
Mis-randomized participants	Mis-randomized participants are those who were not qualified for randomization and who did not take study treatment, but have been inadvertently randomized into the study
Off-site	Describes trial activities that are performed at remote location by an off-site healthcare professional, such as procedures performed at the participant's home.
Other treatment	Treatment that may be needed/allowed during the conduct of the study (i.e. concomitant or rescue therapy)
Participant	A trial participant (can be a healthy volunteer or a patient)
Participant number	A unique number assigned to each participant upon signing the informed consent. This number is the definitive, unique identifier for the participant and should be used to identify the participant throughout the study for all data collected, sample labels, etc.
Period	The subdivisions of the trial design (e.g., Screening, Treatment, Follow-up) which are described in the Protocol. Periods define the study phases and will be used in clinical trial database setup and eventually in analysis
Personal data	Participant information collected by the Investigator that is coded and transferred to Novartis for the purpose of the clinical trial. This data includes participant identifier information, study information and biological samples.

Premature participant withdrawal	Point/time when the participant exits from the study prior to the planned completion of all study drug administration and/or assessments; at this time all study drug administration is discontinued and no further assessments are planned
Randomization number	A unique identifier assigned to each randomized participant
Remote	Describes any trial activities performed at a location that is not the investigative site.
Run-in Failure	A participant who is screened but not randomized/treated after the run-in period (where run-in period requires adjustment to participant's intervention or other treatment)
Screen Failure	A participant who did not meet one or more criteria that were required for participation in the study
Source Data/Document	Source data refers to the initial record, document, or primary location from where data comes. The data source can be a database, a dataset, a spreadsheet or even hard-coded data, such as paper or eSource
Start of the clinical trial	The start of the clinical trial is defined as the signature of the informed consent by the first participant
Study treatment	Any drug or combination of drugs or intervention administered to the study participants as part of the required study procedures; includes investigational drug(s), control(s) or background therapy
Study treatment discontinuation	When the participant permanently stops taking any of the study drug(s) prior to the defined study treatment completion date (if any) for any reason; may or may not also be the point/time of study discontinuation
Tele-visit	Procedures or communications conducted using technology such as telephone or video- conference, whereby the participant is not at the investigative site where the Investigator will conduct the trial.
Treatment arm/group	A treatment arm/group defines the dose and regimen or the combination, and may consist of 1 or more cohorts.
Treatment of interest	The treatment of interest and, as appropriate, the alternative treatment to which comparison will be made. These might be individual interventions, combinations of interventions administered concurrently, e.g. as add-on to standard of care, or might consist of an overall regimen involving a complex sequence of interventions. This is the treatment of interest used in describing the related clinical question of interest, which might or might not be the same as the study treatment.
Variable (or endpoint)	The variable (or endpoint) to be obtained for each participant that is required to address the clinical question. The specification of the variable might include whether the participant experiences an intercurrent event.
Withdrawal of consent	Withdrawal of consent from the study occurs when the participant explicitly requests to stop use of their data and/or biological samples AND no longer wishes to receive study treatment, AND does not agree to further protocol required assessments. This request should be in writing (depending on local regulations) and recorded in the source documentation. This request should be distinguished from a request to discontinue the study. Other study participant's privacy rights are described in the corresponding informed consent form.

10.3 Appendix 3: Clinical laboratory tests

10.3.1 Clinically notable laboratory values

The following criteria will be used to define notable abnormalities of key laboratory tests.

Clinically notable values will be forwarded to Novartis at the same time that they are sent to Investigators.

Any action based on these laboratory values should be discussed with Novartis personnel.

Page 103 of 107 Protocol No. CAIN457O12301

No specific action is pre-defined within this protocol in response to specific abnormal laboratory values; any action taken will be at the discretion of the Investigator or treating physician, taking into account the overall status and medical history of the participant.

Liver Function

 $ALT: > 3 \times ULN$ $AST: > 3 \times ULN$

Alkaline phosphatase (ALP): $> 2.5 \times ULN$

Total bilirubin: > 2 x ULN

Renal Function

Creatinine: > 2 x ULN

Hematology

Hemoglobin: ≥ 2 g/dl decrease from baseline

Platelet count: <100x10E9/L

White blood cell count: < 0.8 x LLN

Neutrophils: < 0.9 x LLN

10.4 **Appendix 4: Participant Engagement**

The following participant engagement initiatives are included in this study and will be provided, as available, for distribution to study participants at the time points indicated. If compliance is impacted by cultural norms or local laws and regulations, sites may discuss modifications to these requirements with Novartis.

- Trial Feedback Questionnaires end of trial
- Patient expert engagement (indication agnostic)

10.5 **Appendix 5: Liver safety monitoring**

To date, there has been no safety signal for liver toxicity with secukinumab in over 29,000 subjects who received at least one dose of secukinumab in a clinical trial (IB Ed 22). From a mechanism of action standpoint there is no known effect of blocking IL-17A on the liver.

Standard liver function tests will be obtained at regular intervals, but special measures for liver safety monitoring are not planned.

All participants with laboratory tests resulting in clinically significant abnormal values (see Section 10.3 for notable laboratory values) are to be followed as per Investigator's discretion until the values return to normal ranges or until a valid reason, other than treatment related AE, is defined.

## List of abbreviations

pharmacokinetic(s)
Proof of Concept

PoC

LIST OF a	poreviations
ADA	Anti-Drug Antibodies
AE	Adverse Event
ALP	Alkaline Phosphatase
ALT	Alanine Aminotransferase
AST	Aspartate Aminotransferase
ATC	Anatomical therapeutic chemical
BMI	Body Mass Index
BSL	Baseline
CMQ	Customized MedDRA Query
CRF	Case Report/Record Form (paper or electronic)
CRS	Case Retrieval Sheet
CSR	Clinical study report
CTCAE	Common Terminology Criteria for Adverse Events
CV	Coefficient of Variation
DBL	Database Lock
DMS	Document Management System
EudraCT	European Clinical Trials Database
FAS	Full Analysis Set
FDA	Food and Drug Administration
GGT	Gamma Glutamyl Transferase
HDL	High Density Lipoprotein
ICE	Intercurrent Event
IG	Immunogenicity
IRT	Interactive Response Technology
ITT	Intent-to-Treat
LDL	Low Density Lipoprotein
LLN	Lower Limit of Normal
LLOQ	Lower Limit of Quantification
LLQ	Lower Level of Quantification
MAR	Missing At Random
MedDRA	Medical Dictionary for Regulatory Activities
mg	milligram(s)
MI	Multiple Imputation
NMQ	Novartis MedDRA Query
NovDTD	Novartis Drug and Therapy Dictionary
NRS	Numerical Rating Scale
NSAIDs	Non-Steroidal Anti-Inflammatory Drug
PAP	Psychometric Analysis Plan
PD	Pharmacodynamic(s)
	Protocol Deviation

PRO	Patient Reported Outcomes
PROMIS	Patient Reported Outcomes Measurement Information System
PSD	Physical Symptom Domain
PT	Preferred term
Q4w	Quaque (every) four weeks
QAP	Qualitative Analysis Plan
QoL	Quality of Life
RAS	Randomized Analysis Set
RCT	Rotator Cuff Tendinopathy
RMP	Risk Management Plan
SAE	Serious Adverse Event
SAF	Safety Set
SAP	Statistical Analysis Plan
SAS	Statistical Analysis Software
S.C.	subcutaneous
SD	Standard Deviation
SF	Short Form
SoC	Standard of Care
SOC	System Organ Class
SMQ	Standardized MedDRA Query
TBL	Total Bilirubin
ULN	Upper Limit of Normal
ULQ	Upper Level of Quantification
VAS	Visual Analog Scale
VS.	Versus
WORC	Western Ontario Rotator Cuff Index

#### 1 Introduction

The scope of this plan includes the primary and secondary analyses. The purpose of this amendment is to modify the analysis plan to reflect the early termination status of the study. At the time of termination, 21 patients had been randomized and 2 patients had completed the study. Patients who were screened by May 7, 2024 were permitted to continue in the study per protocol to study completion.

## 1.1 Study design

CAIN457O12301 is a randomized, double-blind, placebo-controlled Phase III study over 24 weeks in participants with moderate to severe Rotator Cuff Tendinopathy (RCT), refractory to Standard of Care (SoC) (Non-Steroidal Anti-Inflammatory Drugs (NSAIDs) course as per local standard practice, if not intolerant or contraindicated, and a course of physiotherapy over a period of 8 weeks).

A screening period of up to maximum of 56 days will be used to assess participant eligibility. During the 2-week run-in period prior to the Baseline (BSL) visit, the participant will need to have 2 weeks of stable NSAID intake and standardized physiotherapy.

During Study period 1 (BSL to Week 16), double-blinded treatment is administered over 12 weeks, reflecting 16 weeks of total drug exposure. Approximately 234 eligible participants were planned to be randomized at BSL in a 1:1 ratio to one of the following arms:

- Arm 1 (N=117): secukinumab 300 mg s.c. at Day 1 and Weeks 1, 2, 3, 4, 8, and 12
- Arm 2 (N=117): placebo at Day 1 and Weeks 1, 2, 3, 4, 8, and 12

Randomization will be stratified by tear status (no tear/partial tear).

The last dose of study treatment will be administered at Week 12; the primary outcome assessments will be performed at Week 16.

#### **Study Period 1 (Baseline to Week 16)**

Participants should continue on stable NSAID pain medication and a standardized physiotherapy regimen. Reduction in NSAID dose is permitted after BSL, but participants must not increase above dose established during run-in. Use of corticosteroid injections is not permitted during this time.

#### **Study Period 2 (Follow up period)**

A follow-up period (Study period 2) of 8 weeks after the end of the treatment period is planned to assess the maintenance of effect and collect follow-up safety data up to Week 24.

Participants should continue on stable NSAID therapy and physiotherapy during this period. Reduction in NSAID dose is permitted, but participants must not increase above dose established during run-in. Corticosteroid injections are also not permitted after Week 16.

Placebo dose

[figure not shown]

Figure 1-1 Study Design

## 1.2 Study objectives, endpoints and estimands

The purpose of this study is to demonstrate the efficacy and safety of secukinumab 300 mg s.c. in participants with moderate to severe RCT.

Randomisation (1:1)

Due to the early termination of the study, purely descriptive analyses will be performed for primary and secondary endpoints. Exploratory endpoints will not be analyzed.

The objectives and related endpoints are presented in Table 1-1.

Table 1-1 Objectives and related endpoints

Objective(s)	Endpoint(s)			
Primary objective(s)	Endpoint(s) for primary objective(s)			
Demonstrate that the efficacy of secukinumab 300 mg s.c., is superior to placebo, in improving physical shoulder symptoms in participants with moderate to severe RCT at Week 16	Change from BSL in the WORC PSD score at Week 16			
Secondary objective(s)	Endpoint(s) for secondary objective(s)			
Demonstrate that the efficacy of secukinumab 300 mg s.c. is superior to placebo, in achieving a clinically meaningful response in improving physical shoulder symptoms in participants with moderate to severe RCT at Week 16	
 
Proportion of participants who achieve an improvement (increase) of at least 40 points from BSL in WORC PSD at Week 16
 
			

 
Demonstrate that the efficacy of secukinumab 300 mg s.c. is superior to placebo, in participants with moderate to severe RCT at Week 16 as measured by RCT-related QoL
 
	
 
Proportion of participants who achieve an improvement (increase) of at least 50 points from BSL in the WORC total score at Week 16
 
			

 
Demonstrate that the efficacy of secukinumab 300 mg s.c. is superior to placebo, in improving upper extremity in participants with moderate to severe RCT at Week 16
 
	
 
Change from BSL in Patient-Reported Outcomes Measurement Information System (PROMIS) - Short Form (SF) Upper Extremity score at Week 16
 
			

Objective(s)	Endpoint(s)
Demonstrate the efficacy of secukinumab 300 mg s.c. is superior to placebo, to improve physical symptoms at Week 24	Proportion of participants who achieve an improvement (increase) of at least 40 points from BSL in WORC PSD at Week 24
	
 
Change from BSL in WORC PSD score at Week 24
 

 
Evaluate the pharmacokinetics (PK) of secukinumab 300 mg s.c., in the population of participants with moderate to severe RCT
 
	
 
Secukinumab serum concentrations on Day 1 and Week 4 and Week 16
 


 
Evaluate safety, immunogenicity and tolerability of 300 mg s.c. secukinumab, in participants with
 
	
 
Safety and tolerability demonstrated by assessing:
 

moderate to severe RCT	
 
AEs and SAEs (incidence, severity, and relationship with study drug)
 

	
 
Incidence of clinically significant changes in laboratory parameters and vital signs
 

	
 
Incidence of binding and neutralizing anti-drug antibodies (ADAs) at Day 1 and Week 16
 

#### 2 Statistical methods

## 2.1 Data analysis general information

The data will be analyzed by Novartis and/or a designated clinical research organization (CRO). Any data analysis carried out independently by the investigator should be submitted to Novartis before publication or presentation.

Summary statistics for continuous variables will include the number of participants (N), mean, standard deviation (SD), minimum, lower quartile, median, upper quartile and maximum. Summary statistics for discrete variables will be presented in the number and percent of participants in each category.

Missing values will not be imputed and are not included in calculations of summary statistics.

Efficacy and safety data for the 16-week placebo-controlled period or the entire study as appropriate will be presented by the following two treatment groups:

- Secukinumab 300 mg regimen
- Placebo regimen

#### 2.1.1 General definitions

## 2.1.1.1 Study treatment

Study treatment is any drug administered to the study participants as part of the required study procedures, including investigational drug (i.e., Secukinumab 300 mg) and control drug (i.e., placebo).

#### 2.1.1.2 Study Day 1 and other study days

The first day of administration of randomized study treatment (first dose) is defined as *Study Day 1* or *Day 1*.

Of note, if there has been no drug administration, the randomization day is defined as Day 1.

All other study days will be labeled relative to Day 1. For event dates on or after Day 1, study day for a particular event date is calculated as [Date of event] – [Date of first dose] + 1, i.e., Day 2, Day 3, etc., will be one day, two days, etc., after Day 1, respectively. For the dates before Day 1, study day for an event date is calculated as [Date of event]. [Date of first dose] is a

Day 1, study day for an event date is calculated as [Date of event] – [Date of first dose], i.e., Day -1, Day -2, etc., will be one day, two days, etc., before Day 1, respectively. Duration of an event will be calculated as (Event end date – Event start date + 1).

The descriptor "Day 0" will not be used.

## 2.1.1.3 Screening, baseline and post-baseline definitions

Screening refers to any procedures (e.g., checking inclusion and exclusion criteria) performed prior to the date of first dose of study treatment (for safety analysis) or prior to the randomization date (for efficacy analysis). Per protocol, participant informed consent must be obtained prior to performing any study related activity. The date of signing informed consent is the start date of screening period. Any assessment obtained during the screening period will be labeled screening assessment. Assessments made on Day 1 may occur before or after the randomization or the first dose.

For safety analyses, baseline is the last assessment (including unscheduled visits) obtained (on or) before the first dose (day) of study treatment. All assessments obtained after the first dose (day) of study treatment are considered as post-baseline unless otherwise specified.

Of note, baseline will be derived based on the randomization day or first dose day, exact randomization/dosing time is not considered. If a scheduled baseline assessment value is missing, the screening value will be used instead.

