6.4 Study treatment compliance

The Investigator should promote compliance by instructing the participant to attend the study visits as scheduled and by stating that compliance is necessary for the participant's safety and

the validity of the study. The participant should be instructed to contact the Investigator if he/she is unable for any reason to attend a study visit as scheduled.

Off-site treatment administration compliance will be assessed by the Investigator in consultation with the participant as per standard process and regulations. Compliance is expected to be 100%, unless temporary treatment interruption is needed for safety reasons. Compliance will also be assessed by a Novartis monitor using information provided by the authorized site personnel.

All dates and times of study treatment administration will be recorded on the appropriate Dosage Administration Record eCRF page.

Pharmacokinetic parameters (measures of treatment exposure) will be determined in all participants treated with secukinumab, as detailed in pharmacokinetics section.

Drugs administered prior to start of treatment and other drugs/procedures continuing or started during the study treatment period will be entered in the Prior/Concomitant medications or Significant non-drug therapies eCRF page.

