8.4 Safety assessments

Safety assessments are specified below with Section 1.3 Schedule of Activities detailing when each assessment is to be performed.

For details on AE collection and reporting, refer to the Section 8.6.

Evaluation of all AEs and SAEs including injection site reactions, physical examination, vital signs and laboratory assessments will occur. Anti-secukinumab antibody development (immunogenicity) will also be evaluated.

All blood draws and safety assessments should be done prior to study treatment administration. Appropriate safety assessments (e.g., evaluation of AEs and SAEs including injection site reactions) should be repeated after the dose is administered.

- Physical examination
- Height and weight
- Vital signs
- Laboratory evaluations (Hematology, Clinical Chemistry)
- Evaluation of AE/SAEs
- Pregnancy
- Tolerability of secukinumab
- Immunogenicity

As per Section 4.5, during a public health emergency as declared by local or regional authorities i.e. pandemic, epidemic or natural disaster, that limits or prevents on-site study visits, regular phone or virtual calls can occur (according to visit schedule or more frequently if needed) for

Page **61** of **107**

Protocol No. CAIN457O12301

safety monitoring and discussion of the participant's health status until it is safe for the participant to visit the site again.

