8.5.1.2 Participant diary

Participants will be asked to complete an e-diary and paper diary during the periods outlined in Table 1-1.

E-Diary

The e-diary will be given to all participants at Screening. They will complete entries at home starting during the run-in period.

and other indicated visits (see below for further details regarding schedule of recording data and Table 1-1 and Figure 8-1).

The device will remind the participants to complete the questions; however, the site staff must make a telephone call to each participant at the start of the run-in period (two weeks prior to their scheduled BSL visit) to remind them to charge and switch on the device, and to in order for the respective inclusion criteria to be evaluated on the day of the BSL visit. Therefore, it is extremely important that participants adhere to entering in the data prior to BSL.

Site will also contact the participant on the

[figure not shown]
day before they are due to start filling in information into the e-diary in order to remind them to ensure compliance.

[figure not shown]
Participants must bring their e-diaries with them to every scheduled visit. The participant e-diary will be checked by a designated study staff member at each visit; in case of an incomplete e-dairy entry, the study site staff will counsel the participant on the correct use and frequency of the participant e-diary.

Entries starting during the run-in period prior to the scheduled BSL visit and continued throughout study:

WORC Physical Symptoms Domain.

Participants will record their responses to the WORC PSD questionnaire
the scheduled BSL visit and visits indicated, and every visit
capturing WORC data as indicated in Table 1-1.
. These data should be recorded ideally in the evening.

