White blood cell decreased	<lln -="" 10e9
/L</lln>	<3.0 - 2.0 × 10e9 /L	<2.0 - 1.0 × 10e9 /L	; <1.0 × 10e9 /L
Neutrophil count decreased	<lln -="" 1.5="" 10e9
/L</lln>	<1.5 - 1.0 × 10e9 /L	<1.0 - 0.5 × 10e9 /L	<0.5 × 10e9 /L
Lymphocyte count decreased	<lln -="" 0.8="" ×
10e9/L</lln>	<0.8 - 0.5 × 10e9 /L	<0.5 - 0.2 × 10e9 /L	<0.2 × 10e9 /L
Creatinine increased	>ULN - 1.5 × ULN	>1.5 - 3.0 × ULN	>3.0 - 6.0 × ULN	>6.0 × ULN
TBL increased	>ULN - 1.5 × ULN	>1.5 - 3.0 × ULN	>3.0 - 10.0 × ULN	>10.0 × ULN
GGT increased	>ULN - 2.5 × ULN	>2.5 - 5.0 × ULN	>5.0 - 20.0 × ULN	>20.0 × ULN
ALT increased	>ULN - 3.0 × ULN	>3.0 - 5.0 × ULN	>5.0 - 20.0 × ULN	>20.0 × ULN
AST increased	>ULN - 3.0 × ULN	>3.0 - 5.0 × ULN	>5.0 - 20.0 × ULN	>20.0 × ULN
ALP increased	>ULN - 2.5 × ULN	>2.5 - 5.0 × ULN	>5.0 - 20.0 × ULN	>20.0 × ULN
Glucose increased (Hyperglycemia)	>ULN - 8.9 mmol/L	>8.9 - 13.9 mmol/L	>13.9 - 27.8 mmol/L	>27.8 mmol/L
	>ULN - 7.75	>7.75 - 10.34	>10.34 - 12.92	
Cholesterol high	mmol/L	mmol/L	mmol/L	>12.92 mmol/L
Hypertriglyceridemia	1.71 - 3.42 mmol/L	>3.42 - 5.7mmol/L	>5.7 - 11.4 mmol/L	>11.4 mmol/L

Note 1: Grade 4 Hemoglobin events are defined as life-threatening anemia events and will not be displayed in the table, as a numerical range is not provided in the CTCAE.

Of note, baseline will be defined as last assessment prior to first dose. Participants with abnormal laboratory values will be listed and values outside the normal ranges will be flagged.

The number and percentage of participants with clinically CTCAE grade newly occurring or worsening after baseline (treatment emergent) will be presented. Absolute and relative frequencies will be derived for non-overlap groups: CTCAE grade 1, CTCAE grade 2, CTCAE grade 3, and CTCAE grade 4.

Newly occurring or worsening liver enzyme abnormalities will also be summarized (crude incidence as described in above, including 95% confidence intervals) based on the event criteria given in Table 2-5:

Table 2-5 Liver-related events

Parameter	Criterion
ALT	>3×ULN; >5×ULN; >8×ULN;>10×ULN, >20×ULN
AST	>3×ULN; >5×ULN; >8×ULN >10×ULN; >20×ULN
ALT or AST	>3×ULN; >5×ULN; >8×ULN >10×ULN; >20×ULN
TBL	>1.5×ULN, >2×ULN, >3×ULN,
ALP	>2×ULN, >2.5×ULN, >3×ULN. >5×ULN
ALT or AST & TBL	ALT or AST>3×ULN & TBL >2×ULN;
	ALT or AST >5×ULN & TBL >2×ULN;
	ALT or AST >8×ULN & TBL >2×ULN;
	ALT or AST >10×ULN & TBL >2×ULN
ALP & TBL	ALP >3×ULN & TBL >2×ULN
	ALP >5×ULN & TBL >2×ULN

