## 2.7.4 Other safety data

#### **2.7.4.1 Vital signs**

The summary of vital signs will only include treatment emergent data, which are defined as those vital sign measurements after the first dose of study treatment and up to last dose + 84 days.

Analysis in vital sign measurement using descriptive summary statistics for the change from baseline for each post-baseline visit will be performed. These descriptive summaries will be

presented by vital sign and treatment group. Change from baseline will only be summarized for participants with both baseline and post-baseline values and will be calculated as:

change from baseline = post-baseline value – baseline value

The number and percentage of participants with newly occurring notable vital signs will be presented. Criteria for notable vital sign abnormalities are provided in Table 2-6:

Table 2-6 Criteria for notable vital sign abnormalities

Vital sign (unit)	Notable abnormalities	
Systolic blood pressure (mmHg)	>= 140 mmHg or < 90 mmHg	
Diastolic blood pressure (mmHg)	>=90 mmHg or <60 mmHg	
Pulse (bpm)	> 100 bpm or <60 bpm	

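### SAP 2.1.1.3 sets the safety baseline by calendar day, so a last Day 1 value taken after the first dose becomes the baseline, contradicting SAP 2.7.3 and 2.7.4.1

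*SAP*

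**What the plan says.** SAP 2.1.1.3 accepts that Day 1 assessments can fall on either side of the first dose. For safety analyses it then states that "baseline is the last assessment (including unscheduled visits) obtained (on or) before the first dose (day) of study treatment", and that "All assessments obtained after the first dose (day) of study treatment are considered as post-baseline unless otherwise specified". It closes by noting that "baseline will be derived based on the randomization day or first dose day, exact randomization/dosing time is not considered". Table 2-1 follows the same line. For every group with a visible Baseline window (WORC/PROMIS, PK, immunogenicity, vital signs), that window is ≤ 1 and the next one opens on Day 2.

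Two later sections cut at the dose rather than the day. SAP 2.7.3, on laboratory data: "Of note, baseline will be defined as last assessment prior to first dose". SAP 2.7.4.1 restricts the vital-sign summary to treatment-emergent data, "defined as those vital sign measurements after the first dose of study treatment and up to last dose + 84 days".

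On planned timing, Protocol Table 1-2 (footnote 11) makes the scheduled vital signs, laboratory, PK and immunogenicity collections pre-dose. Protocol 8.4 agrees, and adds that appropriate safety assessments "should be repeated after the dose is administered". Protocol 6.4 states: "All dates and times of study treatment administration will be recorded".

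**The concern.** A baseline should not contain the effect of treatment. Under a calendar-day rule that picks the last record, a value obtained after the injection on Day 1 displaces the valid pre-dose value. Such records are few, but they are likely to exist because something happened after first exposure. A first-dose fall in blood pressure would become the reference instead of a newly occurring notable value, and every later change for that participant would be measured from it.

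The SAP also gives two answers for the same record. A post-dose Day 1 blood pressure is baseline under 2.1.1.3 and treatment emergent under 2.7.4.1. Two programmers working independently could produce different tables and each cite the SAP.

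**Working it through.** **1. Does Table 2-1 put all of Day 1 in Baseline by design?** SAP 2.4.1.1 gives the window algorithm. For an even gap x, the earlier visit ends at its target day + x/2 and the later one starts at its target day − x/2 + 1. For an odd gap, y is x/2 rounded down, and the limits are + y and − y.

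- Vital signs (Group 7), targets 15, 29, 57, 85, 113, 169: 15 + 7 = 22 and 29 − 7 + 1 = 23; 29 + 14 = 43 and 57 − 14 + 1 = 44; 57 + 14 = 71 and 85 − 14 + 1 = 72; 85 + 14 = 99 and 113 − 14 + 1 = 100; 113 + 28 = 141 and 169 − 28 + 1 = 142. All match the table.
- Baseline to Week 1 (Days 1 and 8, gap 7, y = 3): the algorithm would end Baseline at 1 + 3 = Day 4 and start Week 1 at 8 − 3 = Day 5. The table instead ends Baseline at Day 1 and opens Week 1 at Day 2.

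So the table replaces the algorithm with a day boundary. Every Day 1 value, before or after the dose, falls in Baseline, as 2.1.1.3 says.

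**2. How each provision classifies a last Day 1 value taken after the dose**

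| Provision | Data | Classification |
|---|---|---|
| SAP 2.1.1.3 | safety, general | baseline, not post-baseline |
| SAP Table 2-1, Groups 6 and 7 | immunogenicity, vital signs | Baseline window |
| SAP 2.7.3 | laboratory | not baseline |
| SAP 2.7.4.1 | vital signs | treatment emergent |

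The first two rows conflict with the last two. Table 2-2 does not rescue the value: its most-extreme rule for notable abnormalities selects within post-baseline windows, and Day 1 is in none of them.

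**3. Which records can be affected?** Only unscheduled, repeat or mistimed ones, because the scheduled measurements are pre-dose.

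- Table 1-2 footnote 5 makes vital signs mandatory at every unscheduled visit, so a same-day unscheduled visit after dosing would yield one.
- Protocol 8.9 calls for an immunogenicity sample when hypersensitivity is suspected. If taken on Day 1, it could set the baseline ADA status summarized under SAP 2.9.1.

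**4. Illustration (assumed values).** Day 1 systolic pressure is 130 mmHg before the dose and 85 after it; Week 2 is 130.

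- By day (2.1.1.3): baseline = 85; Week 2 change = 130 − 85 = +45. The value below 90 (notable under Table 2-6) is the baseline, not a new occurrence.
- By dosing time: baseline = 130; Week 2 change = 0; 85 is a newly occurring notable value.

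The shift in the arm mean change is 45/n. SAP Section 1 reports 21 randomized at termination, or 21/2 = 10.5 per arm. Participants already screened by the cut-off date could continue, so the final n is not known. For assumed arm sizes of 10, 15 and 20, the shift is 4.5, 3.0 and 2.25 mmHg.

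**5. What is untouched.** Adverse events are treatment emergent from the first dose (SAP 2.7.1), anaphylaxis has its own listing, and SAP 2.7.3 keeps all laboratory and vital-sign records in listings.

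**The case against.** The strongest reply is that this is a wording mismatch with almost no practical reach. The post-baseline sentence in 2.1.1.3 allows for exceptions, and 2.7.3 and 2.7.4.1 can be read as those exceptions. That largely settles the laboratory data, because 2.7.3 states its own baseline. It does not settle vital signs: 2.7.4.1 says which values are treatment emergent but leaves the baseline to 2.1.1.3, so the same record can be both.

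The routes are also narrow, and this stands. The only examples Protocol 8.4 gives of assessments repeated after dosing are adverse events and injection site reactions; vital signs are not named, and none are scheduled post-dose. Footnote 5 concerns unscheduled visits, and a reaction during the Baseline visit is not clearly one. Protocol 8.9 has the participant return to the site for the reaction sample without fixing a day. The blood-pressure figures are hypothetical.

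A reader might also infer that the primary endpoint is affected, since Protocol 8.5.1.2 says of the at-home PSD entries: "These data should be recorded ideally in the evening". The documents do not support that. The last-assessment rule is written for safety analyses, the same protocol section stresses that diary data be entered before the baseline visit, and the exact PSD day pattern is blacked out. No Day 1 evening entry is visible. That the available text gives no selection rule for the efficacy baseline is a separate question.

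**Conclusion.** The point holds for safety data and is small. SAP 2.1.1.3 gives a wrong baseline when the last Day 1 record is post-dose, and it contradicts 2.7.3 and 2.7.4.1. The tables concerned are descriptive: change from baseline, newly occurring notable values and baseline ADA status. How often this occurs cannot be derived from the documents and is probably low; with about 10 participants per arm, though, a single such record could visibly move a mean.

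Two broader inferences should be resisted. It is not true that any post-dose Day 1 value becomes baseline: only the last record of the day does. Nor are the data lost, since laboratory and vital-sign records remain in the listings and reactions are still counted as adverse events. The conclusion assumes that at least one unscheduled, repeat or mistimed post-dose Day 1 record can occur, which the documents allow but do not show.

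**What to change.** Replace the note in SAP 2.1.1.3 with a rule along these lines: safety baseline is the last assessment before the first dose, using date and time where time is recorded; scheduled Day 1 assessments without a time are taken as pre-dose; Day 1 unscheduled or repeat assessments known to be post-dose are post-baseline. Let those Day 1 post-dose values count for notable abnormalities, and align 2.7.3, 2.7.4.1 and the Baseline column of Table 2-1 with the same rule.

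The cost is SAP wording and one condition in the baseline derivation. Dosing times are recorded (Protocol 6.4), as are immunogenicity sample times (Protocol 8.9), and Table 2-2 already uses time to order same-day post-baseline safety values.

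The weak spot is vital signs, for which the documents do not show that a collection time is captured. There the classification would rest on the scheduled/unscheduled flag. That flag is imperfect: Protocol 8.1, for example, allows an out-of-range laboratory value to be repeated before randomization, so a repeat is not always post-dose. The SAP should state the default for untimed unscheduled records.
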